5.1 Full Analysis Set

The full analysis set includes all subjects who have been administered at least one treatment of the IMP and for whom efficacy data after IMP administration are available.

5.2 Safety Analysis Set

The safety analysis set includes all subjects who have been administered at least one treatment of the IMP.

5.3 PK Analysis Set

Includes all subjects who have been administered at least one OPC-131461 and have at least one measurement of plasma drug concentration.

5.4 PD Analysis Set

Includes all subjects who have been administered at least one treatment of the IMP and have evaluable PD data after IMP administration.

5.5 Handling of Missing Data

For missing values, no imputation will be applied.

6 Primary and Secondary Endpoints Analysis

6.1 Primary Endpoint

See Table 2-1.

6.2 Secondary Endpoints

See Table 2-1.

7 Disposition and Demographic Analysis

The following data will be aggregated by treatment group (OPC-131461 by dose and overall) and overall (excluding tabulation of subjects who gave informed consent).

7.1 Subject Disposition

For subjects from whom informed consent is obtained, the number of subjects who provided informed consent and were randomized, and the numbers and percentages of

subjects who did not receive IMP after randomization, subjects who received IMP, subjects who completed the trial after IMP administration (subjects who completed 14-day treatment and subjects who completed the trial early), and subjects who discontinued the trial after IMP administration will be presented (denominator is the number of subjects randomized). The number and percentage of subjects who discontinue IMP administration will be summarized by reason for discontinuation.

For the subjects who were randomized, the number and percentage of subjects included in each analysis set will be summarized.

7.2 Demographic and Baseline Characteristics

For the full analysis set and the safety analysis set Table 7.2-1, descriptive statistics (number of subjects, mean, standard deviation, minimum, median, maximum; the same applies hereinafter up to Section 9) or frequency distribution (number of subjects, %; the same applies hereinafter) will be tabulated.

Table 7.2-1 Demographic and Baseline Characteristics			
Item	Timing	Method	Level
Age (years)	Time of informed consent	Descriptive statistics	–
		Frequency distribution	18-29, 30-39, 40-49, 50-59, 60-69, 70-79, 80-85, 86-89
			<65, ≥65
Sex	–	Frequency distribution	Female, Male
Height (cm)	Screening	Descriptive statistics	–
Weight (kg)	Screening	Descriptive statistics	–
BMI (kg/m ²)	Screening	Descriptive statistics	–
Country where the trial is conducted	–	Frequency distribution	JAPAN
Race	–	Frequency distribution	Asian, American Indian or Alaska Native, Black or African American, Native Hawaiian or Other Pacific Islander, White, Other

Table 7.2-1 Demographic and Baseline Characteristics			
Item	Timing	Method	Level
Ethnicity	–	Frequency distribution	Not Hispanic or Latino, Hispanic or Latino, Unknown
Underlying disease (multiple choice) 
 • Ischemic heart disease • Cardiomyopathy • Valvular disease • Hypertensive heart disease • Arrhythmia 	Screening	Frequency distribution	Yes, No
Heart failure type	Screening	Frequency distribution	Right Heart Failure, Left Heart Failure, Bi-ventricular Failure, Unspecified
Presence or absence of arrhythmia	Screening	Frequency distribution	Yes, No
Presence or absence of pacemaker	Screening	Frequency distribution	Yes, No
Presence or absence of implantable cardioverter defibrillator	Screening	Frequency distribution	Yes, No
Complication (multiple choice) 
 • Hypertension • Angina pectoris • Diabetes mellitus • Renal impairment 	Screening	Frequency distribution	Yes, No
Presence or absence of complications	Screening	Frequency distribution	Yes, No
Presence or absence of medical history	Screening	Frequency distribution	Yes, No

7.3 Baseline Disease Evaluation

Each item at baseline will be tabulated in the full analysis set and the safety analysis set.

Table 7.3-1 Baseline Disease Evaluation

7.4 Treatment Compliance

The full analysis set will be used. Frequency distribution will be determined for presence or absence of the days of IMP not administered.

7.5 Prior and Concomitant Medications

Frequency distributions of the use of concomitant medications and therapies on the starting day of IMP administration will be calculated for the full analysis set and the safety analysis set.

Table 7.5-1 Use of Concomitant Medications and Therapies on the Starting Day of IMP Administration	
Item	Level
Loop diuretics	Loop diuretic alone, Loop diuretic + other diuretic, No loop diuretic
Loop diuretic dose (Furosemide equivalent*)	< 40 mg/day, ≥ 40 to < 80 mg/day, ≥ 80 mg/day, No loop diuretic
Diuretic category *Concomitant use of diuretics other than loop diuretics, thiazide diuretics, or mineralocorticoid receptor antagonists will not be considered	Loop diuretic alone, Loop diuretic + thiazide diuretic, Loop diuretic + mineralocorticoid receptor antagonist, Loop diuretic + thiazide diuretic + mineralocorticoid receptor antagonist, No loop diuretic
Thiazide diuretic	No, Yes
Mineralocorticoid receptor antagonist	No, Yes
Therapeutic drugs for heart failure other than diuretics	No, Yes
Digitalis preparation	No, Yes
ACE inhibitor	No, Yes
βblocker	No, Yes
Angiotensin receptor antagonist	No, Yes
SGLT2 inhibitor	No, Yes
HCN channel blocker	No, Yes
Angiotensin receptor neprilysin inhibitor (ARNI)	No, Yes
Soluble guanylate cyclase (sGC) stimulator	No, Yes
Salt restriction	No, Yes

*The amount equivalent to 40 mg of furosemide is 1 mg of bumetanide, 60 mg of azosemide, and 8 mg of torasemide.

7.6 Protocol Deviations

The frequency distribution of the presence or absence of significant deviations will be calculated for each CRF classification (Dosing, Inclusion/Exclusion Criteria, Met Withdrawal Criteria But Not Withdrawn, Prohibited Concomitant Medications) of the randomized subjects. The frequency distribution of subjects with any significant deviation will also be determined.

8 Efficacy Analyses

The following analyses will be performed using the full analysis set.

8.1 Primary Efficacy Endpoint

The primary endpoint is the change in body weight from baseline (before IMP administration on Day 1) to the last assessment time point (the day after IMP administration) by Day 8.

8.1.1 Primary Efficacy Endpoint Analysis

For the primary analysis, an analysis of covariance model with treatment group as a fixed effect and baseline body weight as a covariate will be used. The least squares mean and two-sided 95% confidence interval (t-distribution) of each dose group will be determined. In addition, the least squares mean difference between OPC-131461 dose groups and the placebo group and two-sided 95% CI (t-distribution) and p-value will be calculated by comparing those groups at a two-sided significance level of 5%. Control of experimental-wise type 1 error per test will not be performed.

Similar analysis will be performed using the primary analysis model excluding baseline body weight.

For the change from baseline in body weight at the last assessment, a bar graph of the least squares mean (two-sided 95% CI [t-distribution]) with the treatment group as the horizontal axis will be prepared for each model.

8.1.2 Sensitivity Analysis

Not performed.

8.1.3 Technical Details of Primary Efficacy Endpoint Analysis

The SAS code for the primary analysis is shown below.

```
proc glm data=DATA;  
  class TRTP;  
  model CHG= TRTP BASE;  
  lsmeans TRTP / cl pdiff=control('CONTROL') adjust=t;  
run;
```

8.2 Key Secondary Efficacy Endpoint

8.2.1 Key Secondary Efficacy Endpoint Analysis

For the key endpoint, in order to investigate the dose-response relationships for placebo, 1, 2, 5, and 10 mg, a model similar to that used in the primary analysis will be used to contrast the response saturated at 1 mg, response saturated at 2 mg, response saturated at 5 mg, and linear response.

Similar analysis will be performed using the primary analysis model excluding baseline body weight.

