Primary Objective: To investigate the dose response in respect of weight decrease following repeated oral administration of OPC-131461 at 1, 2, 5, 10 mg or placebo in patients with CHF with volume overload despite having diuretics other than vasopressin antagonists.	Primary Efficacy Endpoint: Change in body weight from baseline to the last assessment time point (the day after investigational medicinal product [IMP] administration) by Day 8 Secondary Efficacy Endpoints: Change in body weight from baseline to the last assessment time point (the day after IMP administration) by Day 15 Percent change in body weight from baseline to the last assessment time point (the day after IMP administration) by Day 8 Percent change in body weight from baseline to the last assessment time point (the day after IMP administration) by Day 15 Improvement of or change in congestive findings (lower limb edema, pulmonary congestion, jugular venous distention, hepatomegaly, cardiothoracic ratio, pulmonary rales, and cardiac third sound) from the baseline to the last assessment time point (the day of IMP administration) by Day 7 Improvement of or change in congestive findings (lower limb edema, pulmonary congestion, jugular venous distention, hepatomegaly, cardiothoracic ratio, pulmonary rales, and cardiac third sound) from baseline to the last assessment (the day after IMP administration) by Day 15 Congestive findings (lower limb edema, pulmonary congestion, jugular venous distention, hepatomegaly, cardiothoracic ratio, pulmonary rales, and cardiac third sound), time to resolution of congestive findings, and the New York Heart Association (NYHA) Functional Classification

Table 2-1 Trial Objectives and Endpoints	
Objectives	Endpoints

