3.4 Handling of Time Points

Efficacy, safety, and exploratory endpoints will be described (see [Section 11.2](#) for baseline pharmacodynamic endpoints).

The analysis visit used for tabulating each visit will be the CRF visit and time point values. Follow-up examinations for pharmacokinetic endpoints and pharmacodynamic endpoints will not be tabulated. However, the completion/discontinuation test visits will be classified into the following analysis visits.

- End-of-treatment examination in subjects who completed 14-day IMP administration: Day 15
- End-of-treatment examination in early completers: Visit on the applicable day (excluding congestive findings, chest X-ray [cardiothoracic ratio, pulmonary congestion], NYHA classification, and 12-lead ECG [Because these items, which are specified to be measured at a feasible time after IMP administration, are measured after IMP administration during treatment, while for early completers, IMP will not be administered the next day.])
- Withdrawal Examination: Visit at discontinuation (not tabulated as visit of discontinuation)

Post-treatment observation will be classified as Day 16 for patients who have completed 14 days of IMP administration (however, post-treatment observation analysis visits will also be prepared for items other than PK and PD endpoints).

Echocardiography will be classified as “Day 15-16” if it is assessed at the completion/discontinuation test visit or post-treatment observation.

For pulmonary congestion, cardiothoracic ratio, and NYHA classification, if IMP is administered for less than 7 days, the day after IMP administration will be included in the analysis visit “Last assessment by Day 7 (day of IMP administration).”

The baseline of each item is defined as follows.

Table 3.4-1 **Handling of Time Points**

*If there are multiple data in the run-in period, the data closest to Day 1 will be adopted as the baseline.

4 Sample Size

The sample size is set as 31 subjects per group.

Assuming that a dose of OPC-131461 at 5 mg or higher is equivalent to 15 mg of tolvaptan in patients with CHF, the sample size required to demonstrate the superiority of OPC-131461 over placebo in terms of the primary endpoint, ie, the change in body weight from baseline to the last assessment time point (the day after IMP administration) by Day 8, was determined (multiplicity relating to the use of more than one OPC-131461 dose group was not considered).

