8.2.3 Technical Details of Key Secondary Efficacy Endpoint Analysis

The SAS code for examination of dose-response relationship is shown below.

```
proc glm data = DATA;  
  class TRTP;  
  model CHG = TRTP BASE;  
  contrast '1 mg saturated' TRTP 4 -1 -1 -1 -1;  
  contrast '2 mg saturated' TRTP 7 2 -3 -3 -3;  
  contrast '5 mg saturated' TRTP 9 4 -1 -6 -6;  
  contrast 'linear' TRTP 2 1 0 -1 -2;  
run;
```

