10.2 Statistical Methods

- 1) Data on each of the endpoints presented in [Section 10.1 1](#)) will be summarized by compound, treatment group, and day of IMP administration. In addition, data on the endpoints shown in [Section 10.1 1](#)) will be summarized by time point of blood sampling, while data on the endpoints shown in [Section 10.1 2\), 3\), and 4\)](#) will be summarized by parameter. The descriptive statistics to be calculated will include the number of subjects in the analysis set, number of subjects tabulated, arithmetic mean, standard deviation, coefficient of variation, and minimum, median, and maximum values for plasma drug concentration, and the number of subjects in the analysis set, number of subjects tabulated, arithmetic mean, standard deviation, coefficient of variation, geometric mean, and minimum, median, and maximum values for PK parameters. For t_{max} and t_{last} , the arithmetic mean, standard deviation, coefficient of variation, and geometric mean will not be calculated. For λ_z , descriptive statistics will not be calculated.

2) For the endpoints shown in [Section 10.1 5](#)), data will be analyzed by day of IMP administration using regression equation (I) to obtain an estimate of b and its two-sided 95% CI.

$$\ln Y = a + b \cdot \ln X \dots (I)$$

X: Dose

Y: Parameter (C_{\max} and AUC_{24h})

The parameter will be determined to show dose proportionality when the two-sided 95% CI of the estimate of b includes 1.

[figure not shown]

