Appendix 1 List of Summary Tables

CT-1.1 Subject Disposition (Screened Subjects)

CT-1.2 Analysis Set (Randomized Subjects)

CT-2.1 Reasons for Discontinuation (Randomized Subjects)

CT-2.2 Protocol Deviations (Randomized Subjects)

CT-3.1.1 Demographic and Baseline Characteristics (Full Analysis Set)

CT-3.1.2 Demographic and Baseline Characteristics (Safety Analysis Set)

CT-3.2.1 Underlying Disease Leading to Heart Failure (Full Analysis Set)

CT-3.2.2 Underlying Disease Leading to Heart Failure (Safety Analysis Set)

CT-3.2.3 Medical History (Full Analysis Set)

CT-3.2.4 Medical History (Safety Analysis Set)

CT-3.3.1 Baseline Disease Evaluation (Full Analysis Set)

CT-3.3.2 Baseline Disease Evaluation (Safety Analysis Set)

CT-4.1 Concomitant Medications and Therapy Used on the First Day of Investigational Medicinal Product (Full Analysis Set)

CT-4.2 Concomitant Medications and Therapy Used on the First Day of Investigational Medicinal Product (Safety Analysis Set)

CT-5.1 Analysis of Covariance for Change from Baseline in Body Weight to Last Assessment Time Point (the Day After Investigational Medicinal Product Administration) by Day 8 (Full Analysis Set)

CT-5.2 Analysis of Dose Response for Change from Baseline in Body Weight to Last Assessment Time Point (the Day After Investigational Medicinal Product Administration) by Day 8 (Full Analysis Set)

CT-5.3 Analysis of Covariance for Change from Baseline in Body Weight to Last Assessment Time Point (the Day After Investigational Medicinal Product Administration) by Day 15 (Full Analysis Set)

CT-5.4 Analysis of Dose Response for Change from Baseline in Body Weight to Last Assessment Time Point (the Day After Investigational Medicinal Product Administration) by Day 15 (Full Analysis Set)

CT-5.5 Descriptive Statistics for Change from Baseline in Body Weight by Visit (Full Analysis Set)

CT-5.6 Descriptive Statistics for Change Rate from Baseline in Body Weight by Visit (Full Analysis Set)

CT-5.7.1 Subgroup Analysis of Analysis of Covariance for Change from Baseline in Body Weight to Last Assessment Time Point (the Day After Investigational Medicinal Product Administration) by Day 8 (Full Analysis Set)

CT-5.7.2 Subgroup Analysis for Change from Baseline in Body Weight to Last Assessment Time Point (the Day After Investigational Medicinal Product Administration) by Day 8 (Full Analysis Set)

CT-6.1.1 Improvement Rate for Lower Limb Edema and Pulmonary Congestion (Full Analysis Set)

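### Does SAP section 8.2.1 need a written rule for choosing among its four dose-response contrasts?

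*SAP*

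**What the plan says.** The primary objective in SAP Table 2-1 is "To investigate the dose response in respect of weight decrease following repeated oral administration of OPC-131461 at 1, 2, 5, 10 mg or placebo". Two analyses of the Day 8 weight change serve it.

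- **Section 8.1.1** fits an analysis of covariance with treatment group and baseline weight. It gives least squares means with 95% intervals for every group, each dose's difference from placebo with interval and p-value at two-sided 5%, and a bar graph by group. It adds: "Control of experimental-wise type 1 error per test will not be performed".
- **Section 8.2.1** says that, to investigate the dose-response relationships, a similar model "will be used to contrast the response saturated at 1 mg, response saturated at 2 mg, response saturated at 5 mg, and linear response". Section 8.2.3 gives the code, from "contrast '1 mg saturated' TRTP 4 -1 -1 -1 -1" to "contrast 'linear' TRTP 2 1 0 -1 -2".

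Both analyses are repeated without baseline weight, and section 8.3.1 repeats them for Day 15. The contrast results go to table CT-5.2 ("CT-5.2 Analysis of Dose Response for Change from Baseline in Body Weight to Last Assessment Time Point") and its Day 15 counterpart, CT-5.4.

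No sentence says what follows if one, several or all of the contrasts are significant. By comparison, section 10.2 does state a reading rule for the pharmacokinetic parameters: "The parameter will be determined to show dose proportionality when the two-sided 95% CI of the estimate of b includes 1".

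**The concern.** The contrast labels read like hypotheses about where the response levels off. They are not. Each contrast tests the null hypothesis that its own weighted sum of group means is zero, so a significant result says the response is not flat and does not confirm the shape in the label. Because the four overlap heavily, they tend to be significant together, and the labels then contradict one another: saturated at 1 mg, at 2 mg, at 5 mg, or still rising.

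Dose response is the primary objective, and these are the only planned tests that use all five groups at once. With two endpoints, two models and four contrasts there are 2 × 2 × 4 = 16 p-values. Without a written rule, a favoured shape could be picked after unblinding. In the worst case a significant 1 mg contrast would be reported as a plateau at 1 mg although 1 mg does nothing.

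**Working it through.** **Inputs.** Section 4: difference 1.09 kg, SD 1.30, 31 per group, 90% power, two-sided 5%; the tolvaptan-arm SD of 1.61 serves as a sensitivity value. Section 8.2.3: the coefficients. The SAP states no level for the contrasts, so two-sided 5% is assumed. Error degrees of freedom are 155 − 6 = 149, and the critical t is 1.976.

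**The SAP's own figure.** A two-sample t-test with these values has power 0.891 at 30 per group and 0.901 at 31. The stated 31 is reproduced.

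**Coefficients.** All four sets sum to zero and match their labels; linear means equal steps between dose levels. Squared lengths are 20, 80, 170 and 10. With equal groups, the correlation of two contrasts is their inner product divided by the product of their lengths:

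| Pair | Calculation | Correlation |
|---|---|---|
| 1 mg, 2 mg | 35/√(20·80) | 0.875 |
| 1 mg, 5 mg | 45/√(20·170) | 0.772 |
| 1 mg, linear | 10/√(20·10) | 0.707 |
| 2 mg, 5 mg | 110/√(80·170) | 0.943 |
| 2 mg, linear | 25/√(80·10) | 0.884 |
| 5 mg, linear | 40/√(170·10) | 0.970 |

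**Joint significance.** Simulation with 200,000 trials per scenario and maximum effect 1.09 kg:

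| Truth | All four, SD 1.30 | Exactly one, SD 1.30 | All four, SD 1.61 |
|---|---|---|---|
| Saturated at 1 mg | 83% | 3.4% | 64% |
| Saturated at 2 mg | 93% | 0.7% | 76% |
| Saturated at 5 mg | 87% | 0.6% | 68% |
| Linear across dose levels | 73% | 1.9% | 53% |
| Linear in mg | 45% | 6.2% | 31% |
| Only 5 and 10 mg act | 55% | 0.6% | 38% |

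With a maximum effect of 0.80 kg and SD 1.30, all four are significant in 44% to 67% under the coded shapes, 33% if only 5 and 10 mg act, and 26% if linear in mg. With a flat response, at least one is significant in about 9.5%.

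**The misreading case.** Section 4 sizes the trial "Assuming that a dose of OPC-131461 at 5 mg or higher is equivalent to 15 mg of tolvaptan in patients with CHF". Suppose 1 and 2 mg do nothing and 5 and 10 mg have the full effect. The 1 mg contrast then has expected value 2 × 1.09 = 2.18 and standard error 1.30·√(20/31) = 1.044, so its noncentrality is 2.09 and its power is about Φ(2.09 − 1.976) ≈ 0.55. For the 2 mg contrast the figures are 6.54/2.088 = 3.13 and about 0.88. Both agree with the simulation.

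Now take what section 8.1.1 already reports in that case. The 1 mg minus placebo difference has standard error 1.30·√(2/31) = 0.330 kg and interval half-width 1.976 × 0.330 = 0.65 kg, centred on zero on average. Its p-value falls below 0.05 in 5% of trials. Treating the SD as known, the interval excludes −1.09 kg in about Φ((1.09 − 0.65)/0.330) ≈ 91%. The inactive dose is visible in the same set of tables.

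**What a selection rule would bring.** Choosing the contrast with the largest absolute t picks the true shape in 84% (1 mg), 61% (2 mg), 47% (5 mg) and 63% (linear across levels) at SD 1.30. If only 5 and 10 mg act, it picks linear in 71% and saturated at 5 mg in 29%. The reason is geometric: the centred true pattern has squared length 1.2, so its absolute correlation is 3/√(10·1.2) = 0.866 with the linear contrast and 12/√(170·1.2) = 0.840 with the 5 mg contrast. The rule would usually describe a step as a straight line.

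**The case for a change.** The strongest case for a change is that the SAP fixes the coefficients, so their reading belongs beside them. Section 10.2 does this for a pharmacokinetic question, while the primary objective gets less. The disclaimer on type 1 error stands in the section on pairwise comparisons and concerns multiplicity, not what one significant contrast means. If only 5 and 10 mg act, a largest-t rule would pick saturated at 1 mg in about 0.1% of trials, against 55% in which that contrast is significant.

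Much of this stands. The contrasts do not discriminate between shapes, section 8.2.1 does not say so, and a careless report could misuse a label. But section 10.2 announces a determination and so needs a criterion; section 8.2.1 announces none. The protection against a false plateau at 1 mg comes at the price of a wrong linear label in most of the same trials, and the planned group means guard against the same misreading without that price.

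The lesser gaps close on reading. Section 8.1.1 names the model with baseline weight as primary, the code in section 8.2.3 includes it, and the other model is an addition. The scoring of the linear contrast is fixed by the code, which is part of the SAP. Two-sided 5% is the level used in sections 4 and 8.1.1. The 16 p-values and the 9.5% under a flat response follow from an openly stated choice. An adjusted threshold for one overall claim (2.27 for the largest absolute t) would cost 1 to 3 points of power and serve a claim the SAP does not make.

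**Conclusion.** No change to the plan. The contrasts are valid, the coefficients match their labels, and following the SAP as written gives no wrong number. What is missing is a sentence of interpretation that a trial statistician supplies as a matter of course: a significant contrast shows a response that is not flat, and the pattern is read from the least squares means and intervals in CT-5.1 and CF-1.1.

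The overlap is real. All four contrasts are significant in 73% to 93% of trials under the coded shapes at 1.09 kg and SD 1.30, and in 53% to 76% at SD 1.61. It is not the usual result for every plausible truth: for a response linear in mg or confined to 5 and 10 mg, the figure runs from 26% to 55% across the effect sizes and SDs examined.

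The two possible remedies point in opposite directions. One restates output already planned; the other is a debatable trade-off that is right in 47% to 84% of trials under the coded shapes. The conclusion rests on the SAP's wording, which investigates dose response and selects no shape, and on the assumed two-sided 5% level per contrast. It would be different if the SAP tied dose selection or a claimed plateau to these p-values.
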